7.2. Subject Exclusion Criteria

1. Is pregnant (ie, has a positive pregnancy test) or breastfeeding at screening or Day -5 or is planning to become pregnant during the study period
2. Has a positive urine drug screen for methadone at screening or Day -5

3. Has a positive urine drug screen for opiates or oxycodone at screening or Day -5
 4. Has used naltrexone (oral or VIVITROL) within the 90 days prior to Day -5
 5. Has used methadone within the 30 days prior to Day -5
 6. Has a history of seizures (with the exception of febrile seizures), or has received anticonvulsant therapy during the past 5 years for treatment of seizures (use of anticonvulsant during past detoxification is not exclusionary)
 7. Has a condition, disease state, previous medical history or observed abnormalities (including physical examination, electrocardiogram [ECG], laboratory evaluation [eg, kidney or liver function test result] or urinalysis finding) at screening that, in the opinion of the investigator, would preclude safe participation in the study or interfere with the study assessments, including, but not limited to, the following:
 - Uncontrolled hypertension, uncontrolled diabetes, renal disease/impairment, stroke or neurological disorder, AIDS indicator disease, cardiovascular (eg, endocarditis), neoplastic disease (excluding adequately treated skin cancer or carcinoma in situ of the cervix), chronic pain condition requiring ongoing opioid analgesia
 - Aspartate aminotransferase or alanine aminotransferase value ≥ 3 times the upper limit of normal
 - Treatment for an active TB infection
 - Oral cavity pathology that would interfere with sublingual absorption
 - Significant hypotension below 90/60 and pulse below 60 bpm
 - Any contraindicated medical condition per the approved labeling for either BUP or naltrexone
 8. Has any of the following psychiatric conditions per DSM-5 criteria, as assessed by the MINI:
 - Diagnosis of schizoaffective disorder or bipolar disorder; or current, untreated or unstable major depressive disorder (subjects with current, but stable depression, depressive symptoms or major depressive disorder may be eligible provided bipolar disorder and schizoaffective disorder have been ruled out)
 - Diagnosis within the past 12 months of other psychiatric conditions or disorders that, in the investigator's opinion, could interfere with participation in the study
 9. Is currently physiologically dependent on any psychoactive substance (except opioids, caffeine or tobacco) requiring medical intervention for detoxification
 - Breathalyzer alcohol test positive at Day -5 will be exclusionary; a positive breathalyzer test during screening may be repeated, provided that one negative test is obtained by Day -5
 - Benzodiazepine dependence will be confirmed by positive urine drug screen and investigator judgment during screening
-

10. Has a history of hypersensitivity or adverse reaction to BUP, naltrexone, VIVITROL or naloxone
11. Has a history of more than 3 unsuccessful inpatient or medically assisted outpatient opioid detoxifications during the subject's lifetime
12. Has had significant suicidal ideation or behavior within the past year, confirmed by a baseline Columbia-Suicide Severity Rating Scale (C-SSRS) response of "Yes" to questions 4 or 5
13. Is currently participating in or has participated in a clinical trial of an investigational drug, device or biologic, within 3 months prior to screening
14. Has a history of accidental drug overdose (defined as an episode of opioid-induced unconsciousness or incapacitation) in the past 12 months, whether or not medical treatment was sought or received
15. Is court mandated to receive treatment for opioid use disorder
16. Is employed by the investigator or study center, with direct involvement in the proposed study or other studies under the direction of that investigator or study center, or immediate family* member of the employees or the investigator
17. Is employed by the sponsor or contract research organization (CRO; permanent, temporary contract worker or designee responsible for the conduct of the study), or immediate family* member of a sponsor or CRO employee

* Immediate family is defined as a spouse, parent, sibling or child, whether biological or legally adopted.

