8.8.11.4. Columbia Suicide Severity and Rating Scale

The C-SSRS is a questionnaire administered by a qualified clinician that assesses suicidal ideation and behavior (Posner et al, 2011). The "Baseline/Screening" version of the scale will be administered at the screening visit. The "Since Last Visit" version will be administered at all other timepoints specified in Table 4. Samples of the C-SSRS can be found in Appendix B.

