APPENDIX B. COLUMBIA-SUICIDE SEVERITY RATING SCALE

- Baseline/Screening
- Since Last Visit

COLUMBIA-SUICIDE SEVERITY RATING SCALE (C-SSRS)

Baseline/Screening Version

Version 1/14/09

*Posner, K.; Brent, D.; Lucas, C.; Gould, M.; Stanley, B.; Brown, G.; Fisher, P.; Zelazny, J.;
Burke, A.; Oquendo, M.; Mann, J.*

Disclaimer:

This scale is intended for use by trained clinicians. The questions contained in the Columbia-Suicide Severity Rating Scale are suggested probes. Ultimately, the determination of the presence of suicidality depends on clinical judgment.

*Definitions of behavioral suicidal events in this scale are based on those used in **The Columbia Suicide History Form**, developed by [name] and [name], Conte Center for the Neuroscience of Mental Disorders (CCNMD), New York State Psychiatric Institute, [name]. (Oquendo M. A., Halberstam B. & Mann J. J., Risk factors for suicidal behavior: utility and limitations of research instruments. In M.B. First [Ed.] Standardized Evaluation in Clinical Practice, pp. 103 -130, 2003.)*

For reprints of the C-SSRS contact PPD [redacted] New York State Psychiatric Institute, [name]; inquiries and training requirements contact PPD [redacted]

SUICIDAL IDEATION			Lifetime: Time He/She Felt Most Suicidal	Past ___ Months

Ask questions 1 and 2. If both are negative, proceed to “Suicidal Behavior” section. If the answer to question 2 is “yes,” ask questions 3, 4 and 5. If the answer to question 1 and/or 2 is “yes”, complete “Intensity of Ideation” section below.
				

1. Wish to be Dead Subject endorses thoughts about a wish to be dead or not alive anymore, or wish to fall asleep and not wake up. Have you wished you were dead or wished you could go to sleep and not wake up?
 
If yes, describe:
			Yes No  	Yes No  

2. Non-Specific Active Suicidal Thoughts General non-specific thoughts of wanting to end one’s life/commit suicide (e.g. “I’ve thought about killing myself”) without thoughts of ways to kill oneself/associated methods, intent, or plan during the assessment period. Have you actually had any thoughts of killing yourself?
 
If yes, describe:
			Yes No  	Yes No  

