
3. Active Suicidal Ideation with Any Methods (Not Plan) without Intent to Act Subject endorses thoughts of suicide and has thought of at least one method during the assessment period. This is different than a specific plan with time, place or method details worked out (e.g. thought of method to kill self but not a specific plan). Includes person who would say, “I thought about taking an overdose but I never made a specific plan as to when, where or how I would actually do it....and I would never go through with it”. Have you been thinking about how you might do this?
 
If yes, describe:
			Yes No  	Yes No  

4. Active Suicidal Ideation with Some Intent to Act, without Specific Plan Active suicidal thoughts of killing oneself and subject reports having some intent to act on such thoughts, as opposed to “I have the thoughts but I definitely will not do anything about them”. Have you had these thoughts and had some intention of acting on them?
 
If yes, describe:
			Yes No  	Yes No  

5. Active Suicidal Ideation with Specific Plan and Intent Thoughts of killing oneself with details of plan fully or partially worked out and subject has some intent to carry it out. Have you started to work out or worked out the details of how to kill yourself? Do you intend to carry out this plan?
 
If yes, describe:
			Yes No  	Yes No  
INTENSITY OF IDEATION				

The following features should be rated with respect to the most severe type of ideation (i.e., 1-5 from above, with 1 being the least severe and 5 being the most severe). For prior to study entry, ask about time he/she was feeling the most suicidal.
 
Lifetime - Most Severe Ideation: _____ <small>Type # (1-5) Description of Ideation</small>
 
Past X Months - Most Severe Ideation: _____ <small>Type # (1-5) Description of Ideation</small>
			Most Severe	Most Severe

Frequency How many times have you had these thoughts? (1) Less than once a week (2) Once a week (3) 2-5 times in week (4) Daily or almost daily (5) Many times each day
			____	____

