Actual Attempt: A potentially self-injurious act committed with at least some wish to die, as a result of act . Behavior was in part thought of as method to kill oneself. Intent does not have to be 100%. If there is any intent/desire to die associated with the act, then it can be considered an actual suicide attempt. There does not have to be any injury or harm , just the potential for injury or harm. If person pulls trigger while gun is in mouth but gun is broken so no injury results, this is considered an attempt. Inferring Intent: Even if an individual denies intent/wish to die, it may be inferred clinically from the behavior or circumstances. For example, a highly lethal act that is clearly not an accident so no other intent but suicide can be inferred (e.g. gunshot to head, jumping from window of a high floor/story). Also, if someone denies intent to die, but they thought that what they did could be lethal, intent may be inferred. Have you made a suicide attempt? Have you done anything to harm yourself? Have you done anything dangerous where you could have died? What did you do? Did you _____ as a way to end your life? Did you want to die (even a little) when you _____? Were you trying to end your life when you _____? Or Did you think it was possible you could have died from _____? Or did you do it purely for other reasons / without ANY intention of killing yourself (like to relieve stress, feel better, get sympathy, or get something else to happen)? (Self-Injurious Behavior without suicidal intent) If yes, describe:		Yes No   Total # of Attempts _____	Yes No   Total # of Attempts _____		
Has subject engaged in Non-Suicidal Self-Injurious Behavior?		Yes No  	Yes No  		

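### Exclusion 12 covers past-year suicidal behavior, but its only confirmation test is two C-SSRS ideation items, so behavior recorded without a yes to either item falls within its scope and fails its test

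*Protocol*

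**What the plan says.** Section 7.2, exclusion 12, sets its scope as "Has had significant suicidal ideation or behavior within the past year". It then gives one way of establishing this: "confirmed by a baseline Columbia-Suicide Severity Rating Scale (C-SSRS) response of 'Yes' to questions 4 or 5". No behavior item is mentioned.

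Section 8.8.11.4 fixes the form. The Baseline/Screening "version of the scale will be administered at the screening visit", and a sample is in Appendix B.

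On that form the only numbered questions are 1 to 5, all under the Suicidal Ideation heading. Question 4 is "Active Suicidal Ideation with Some Intent to Act, without Specific Plan"; question 5 is "Active Suicidal Ideation with Specific Plan and Intent". The instruction at the top of the block begins "Ask questions 1 and 2. If both are negative, proceed to" and directs the rater to the behavior section. Questions 3 to 5 are asked only when question 2 is answered yes.

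The Suicidal Behavior block follows, with its own yes/no boxes for actual, interrupted and aborted attempts and for preparatory acts, plus a summary item on whether any suicidal behavior was present. Its probes include "Have you made a suicide attempt? Have you done anything to harm yourself". None of these items carries the number 4 or 5.

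**The concern.** The criterion names two things to exclude, ideation and behavior, but the test attached to it can register only the first. Behavior is picked up only when the same subject also endorses serious ideation on question 4 or 5.

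This concerns who is enrolled. Subjects go through a buprenorphine taper and opioid withdrawal, and section 12 lists the C-SSRS among the safety assessments. Where scope and test disagree, a site applying the scope would exclude a subject whom a site applying the test would accept, and the protocol does not say which governs. An eligibility rule has to be settled in the protocol; an analysis plan cannot repair it afterwards.

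**Working it through.** No figure in the protocol bears on this point, so the check sets the texts side by side.

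**Step 1: what the test can see.** The test reads questions 4 and 5. By their titles in Appendix B, both are active-ideation items. The four behavior categories and the summary item are recorded elsewhere on the form and are not cited in exclusion 12.

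**Step 2: scope against test.** For a past-year look-back there are four cases:

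| Question 4 or 5 | Behavior block | Within stated scope? | Meets stated test? |
|---|---|---|---|
| Yes | Yes | Yes | Yes |
| Yes | No | Yes | Yes |
| No or not asked | Yes | Yes, if the behavior is significant | **No** |
| No or not asked | No | No | No |

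The two halves of the criterion disagree only in the third row.

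**Step 3: whether the third row can occur.** The form allows it in two ways.

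- *Skip rule.* If questions 1 and 2 are both negative, the rater moves to the behavior block and questions 4 and 5 are never put. An attempt can still be recorded there.
- *Inferred intent.* The actual-attempt item lets the rater infer intent from the act or its circumstances when the subject denies it. Such a subject may well answer no to questions 4 and 5, which ask about intent directly.

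**Step 4: whether the confirmation wording is meant loosely.** Inclusion 6 uses the same kind of wording to introduce required proof of buprenorphine maintenance. Exclusion 9 confirms benzodiazepine dependence by a urine screen together with investigator judgment. Where the protocol wants judgment added to a confirmation rule it says so; exclusion 12 does not.

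**Step 5: whether another criterion closes the gap.**

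- Exclusion 14 covers overdose in the past 12 months, but only accidental overdose.
- Exclusion 7 (medical history and findings) and the second part of exclusion 8 (other psychiatric diagnoses within 12 months) turn on the investigator's opinion, and neither names suicidal behavior.
- The MINI, given at screening, asks about suicide attempts and marks those within 12 months as current. No criterion makes that answer exclusionary in itself.

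The gap in row three therefore remains, with discretionary cover only.

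**The case against.** The strongest reply is that few subjects will ever fall in row three. The form defines an actual attempt as involving at least some wish to die, and question 4 asks about suicidal thoughts with some intention of acting on them, so many people with a recent attempt would answer yes to question 4 and be excluded as intended. The ideation block has a lifetime column and a past-period column and does not ask only about the present. Denying current ideation is therefore not enough to skip questions 4 and 5; to skip them altogether a subject must also deny ideation over a lifetime. The MINI puts past-year attempts in front of the investigator, who has grounds under exclusions 7 and 8 to decline the subject. All of this stands. It limits the size of the gap but does not make the criterion's test match its scope.

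Two stronger readings are tempting, and the protocol does not support either.

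- A reader might infer that a recent suicide attempt in general escapes exclusion 12. It does not; only behavior without an accompanying yes to question 4 or 5 does.
- A reader might infer that the post-baseline C-SSRS results would be compromised. Visits after screening use the Since Last Visit version (section 8.8.11.4), and section 13.5 tabulates post-baseline responses by randomized group, so an attempt before screening is not counted there.

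**Conclusion.** The point holds as a mismatch within one eligibility criterion. Exclusion 12 states that it covers suicidal behavior, but the test it names cannot register behavior on its own. The conclusion rests on reading the confirmation clause as the operative rule, which is how the protocol uses such clauses elsewhere, and on the Appendix B sample being the form used.

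The size cannot be given. The protocol has no figure for how often past-year behavior occurs without a yes to question 4 or 5, so any count of affected subjects would be a guess. It is probably small, for the reasons set out under the objection. The primary endpoint, sample size and blinding are untouched. It is a safety-related wording correction, worth making because it is cheap and because the present text gives two answers for the same subject.

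**What to change.** Reconcile exclusion 12 with Appendix B. The confirmation rule should refer to the Suicidal Behavior section of the baseline C-SSRS over the past year, as well as to ideation questions 4 and 5. The criterion is limited to significant ideation or behavior, so the sponsor should state which behavior items meet that description. Making every item, preparatory acts included, automatically exclusionary would set a clinical threshold that the protocol has not stated, and that decision belongs to the sponsor.

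The look-back fields left blank in Appendix B are on sample forms and are not an error; the criterion already fixes one year. The operational form should carry that period for both blocks.

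The cost is a short protocol amendment, with no new assessment because the form is already completed at screening. The downside is possibly a few more screen failures.

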7.3. Subject Withdrawal

Subjects who initiate screening but are not randomized will be considered screen failures. A subject who has previously screen failed may be allowed, at Investigator discretion, to repeat the screening process, provided that the circumstance that led to screen failure is no longer present. A randomized subject who is eligible to receive the naloxone challenge will be considered a treatment completer. Subjects completing all visits during the follow-up period will be categorized as completing the study.

A subject may be discontinued from the study at any time if it is not in the subject's best interest to continue or he/she chooses to withdraw. Reasons for subject withdrawal include:

- AE
- Lack of efficacy
- Withdrawal by subject
- Lost to follow-up
- Pregnancy
- Protocol deviation
- Study terminated by sponsor

- Other

If a subject withdraws or is withdrawn from the study for any reason, any ongoing AEs will be followed until resolution, until deemed stable by the investigator or until the subject is deemed by the investigator to be lost to follow-up. If, in the opinion of the investigator, it is necessary to monitor a subject beyond the last safety follow-up visit, the follow-up period may be extended as necessary. In such instances, the sponsor and the investigator will agree to an acceptable follow-up schedule.

In the event that a subject chooses to withdraw from the study, the investigator should make a reasonable effort to ascertain the reason(s) for withdrawal, while fully respecting the subject's rights. The subject should be encouraged to return to the study center for an early termination (ET) visit, as close as possible to the subject's date of study withdrawal. The ET visit will match the procedures at Day 9 (Table 4). If the subject fails or refuses to return to the study center, an attempt must be made to contact the subject in order to assess as many safety parameters as possible. All data collected remotely must be documented and kept in the subject's record.

The investigator must maintain a record of all subjects who fail to complete the study. The reason for study discontinuation will be entered on the appropriate electronic case report form (eCRF). A subject will be deemed lost to follow-up after 3 attempts at contact have been made. The third attempt at contact must be a certified letter accompanied by a survey inquiring the reason for study discontinuation. All attempts at contact will be documented.

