8.5. Follow-up Period

On Study Days 22 (± 3 days) and 36 (± 3 days), subjects who have completed the Treatment Period and the VIVITROL Induction and Post-VIVITROL Observation Period (Days 1/1a-11) will return to the research center for 2 outpatient follow-up visits that will occur 2 and 4 weeks after the naloxone challenge/VIVITROL injection.

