8.7. Schedule of Visits and Assessments

The schedule of visits and assessments is shown in [Table 4](#).

For a missed visit, the site should attempt to contact the subject to reschedule.

Premature discontinuation procedures are provided in [Section 7.3](#).

Table 4: Schedule of Visits and Assessments

	Screening Period	BUP Lead-in Period			Treatment Period										Naloxone Challenge, VIVITROL, and post-VIVITROL observation			Follow-Up				
Study Visit	1	2	3	4	5										6	7	8	9	10			
Study Day	-26 to -6	-5	-4	-3	-2	-1	1	1a ^a	2	3	4	5	6	7	8	8a ^b	9/ET	10	11	22 (±3 days)	36 (±3 days)	
Informed Consent	X																					
Eligibility Criteria Review	X																					
Demographics and Medical History	X																					
MINI	X																					
MMSE ^c	X						X	X	X	X	X	X	X	X								
MOTYB ^c							X	X	X	X	X	X	X	X								
SMAST	X	X			X															X	X	
Pregnancy Test ^d	X	X					X	X							X	X					X	
Physical Examination ^e	X														X	X						
Height	X																					
Weight	X																					
ECG	X																				X	
Vital Signs ^f	X	X	X	X	X	X	X	X	X	X	X	X	X	X	X	X	X	X	X	X	X	X
Biochemistry, Hematology and Urinalysis Samples	X														X						X	
Breath Alcohol Test	X	X			X																	

Table 4: Schedule of Visits and Assessments (Continued)

	Screening Period	BUP Lead-in Period			Treatment Period													Naloxone Challenge, VIVITROL, and post-VIVITROL observation			Follow-Up	
Study Visit	1	2	3	4	5													6	7	8	9	10
Study Day	-26 to -6	-5	-4	-3	-2	-1	1	1a ^a	2	3	4	5	6	7	8	8a ^b	9/ET	10	11	22 (±3 days)	36 (±3 days)	
Drug Screen ^g	X	X	X	X	X	X	X	X	X	X	X	X	X	X	X	X				X	X	
Residential Admission					X																	
Residential Discharge															X	X						
Randomization ^h						X	X															
Administration of NTX/PBO-N						X ⁱ	X	X	X	X	X	X	X	X	X ⁱ							
Administration of BUP		X	X	X	X	X	X	X	X													
Ancillary Medications ^j					X	X	X	X	X	X	X	X	X	X	X	X	X ^k	X ^k	X ^k			
Naloxone Challenge															X	X						
VIVITROL Injection															X	X						
QSUI	X	X	X	X													X	X	X	X	X	
COWS ^l		X	X	X	X	X	X	X	X	X	X	X	X	X	X ^m	X ^m	X	X	X	X	X	
SOWS ^l		X	X	X	X	X	X	X	X	X	X	X	X	X	X ^m	X ^m	X	X	X	X	X	
Desire for Opioids VAS ^l		X	X	X	X	X	X	X	X	X	X	X	X	X	X	X	X	X	X	X	X	
Pupillometry ⁿ						X	X	X	X	X	X	X	X	X	X	X						

Table 4: Schedule of Visits and Assessments (Continued)

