	Screening Period	BUP Lead-in Period			Treatment Period										Naloxone Challenge, VIVITROL, and post-VIVITROL observation			Follow-Up			
Study Visit	1	2	3	4	5										6	7	8	9	10		
Study Day	-26 to -6	-5	-4	-3	-2	-1	1	1a ^a	2	3	4	5	6	7	8	8a ^b	9/ET	10	11	22 (±3 days)	36 (±3 days)
PGART															X ^o	X ^o	X ^p		X		X
C-SSRS ^q	X	X					X	X		X							X		X	X	X
Psychoeducational Counseling		X	X	X	X	X	X	X	X	X	X	X	X	X	X	X				X	X
HAM-D ^f	X ^s					X														X	X
Cognitive Assessments [†]	X ^s					X														X	X
Prior and Concomitant Medication Review	X	X	X	X	X	X	X	X	X	X	X	X	X	X	X	X	X	X	X	X	X
AE Monitoring	X	X	X	X	X	X	X	X	X	X	X	X	X	X	X	X	X	X	X	X	X

AE=adverse event; ET=early termination; COWS=Clinical Opiate Withdrawal Scale; C-SSRS=Columbia Suicide Severity Rating Scale; ECG=electrocardiogram; HAM-D=Hamilton Rating Scale for Depression; MINI=Mini-International Neuropsychiatric Interview; MMSE=Mini-Mental Status Examination; MOTYB=Months of the Year Backward; NTX=naltrexone; PBO-N=placebo naltrexone; PGART=Patient Global Assessment of Response to Therapy; QSUI=Quantitative Substance Use Inventory; SMAST= Short Michigan Alcohol Screening Test; SOWS=Subjective Opiate Withdrawal Scale; VAS=Visual Analogue Scale

^a Subjects who do not qualify for randomization on Day 1 will receive Day -1 BUP dosing and repeat Day 1 assessments and procedures on the following day, (Day 1a).

^b Subjects who do not qualify to receive VIVITROL on Day 8 will receive Day 7 study drug (naltrexone/PBO-N), and complete Day 7 assessments and procedures. Pre- and postdose COWS will be assessed for clinical safety purposes only. Day 8 assessments and procedures will be repeated the following day (Day 8a).

^c Full MMSE will be conducted at screening. The MMSE orientation questions and MOTYB will be performed 60 (-5/+15) minutes following the second dose of oral naltrexone/PBO-N or at end of testing session for subjects not receiving second dose.

^d For female subjects only. Urine pregnancy tests will be conducted at all specified timepoints; in addition, serum pregnancy tests will be conducted at Screening and Day 1/1a. Urine pregnancy tests to be performed prior to randomization on Day 1/1a and prior to naloxone challenge on Day 8/8a.

- ^c Full physical examination at screening and symptom-driven examinations at subsequent timepoints.

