13.2.1. Study Populations

13.2.1.1. Safety Population

The safety population is defined as all randomized subjects who receive at least 1 dose of naltrexone or PBO-N.

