13.5. Safety and Tolerability Analyses

Safety analyses will be performed using the safety population.

Safety and tolerability will be evaluated based on AEs, vital sign and oxygen saturation measurements, laboratory test results, ECG findings and C-SSRS scores.

Reported AE terms will be coded using the Medical Dictionary for Regulatory Activities (MedDRA).

The incidence of treatment-emergent AEs will be summarized by treatment group and overall by system organ class, and preferred terms within each system organ class. SAEs and AEs resulting in treatment discontinuation will also be summarized. AEs occurring during the treatment period preceding the naloxone challenge will be analyzed separately from AEs occurring on or after the naloxone challenge day.

Change from baseline in laboratory tests, vital signs and oxygen saturation, and ECG assessments (uncorrected QT, QTcF, QTcB, HR, RR and QRS intervals) will be summarized by treatment group and overall at each visit. Number (percentage) of subjects with potentially clinically significant (PCS) values at any postbaseline visit will be also summarized by treatment group.

For each ideation/behavior type in C-SSRS, as well as the overall ideation/behavior category, the number and percentage of subjects with 'Yes' responses at any post baseline visit (including unscheduled visit) will be summarized by treatment group.

Number and percent of subjects initiating concomitant medications, including ancillary medications, during the induction period will be summarized.

Concomitant medications will be categorized and presented using the World Health Organization (WHO) drug Anatomical Therapeutic Chemical (ATC) classification system.

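### A dosed subject who leaves on Days 1-7 has no scheduled post-dose laboratory sample, because the early-termination visit copies Day 9

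*Protocol*

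**What the plan says.** - **ET visit content (7.3):** "The ET visit will match the procedures at Day 9 (Table 4".
- **Laboratory schedule (8.7, Table 4):** the row "Biochemistry, Hematology and Urinalysis Samples" is marked at screening, Day 8 and Day 36. Its cell in the 9/ET column is empty.
- **Who attends Days 22 and 36 (8.5):** "subjects who have completed the Treatment Period and the VIVITROL Induction and Post-VIVITROL Observation Period (Days 1/1a-11) will return to the research center".
- **Safety population (13.2.1.1):** "all randomized subjects who receive at least 1 dose of naltrexone or PBO-N".
- **Laboratory analyses (13.5):** "Change from baseline in laboratory tests, vital signs and oxygen saturation, and ECG assessments" are summarized by treatment group and overall at each visit. The other planned output is "Number (percentage) of subjects with potentially clinically significant (PCS) values at any postbaseline visit", by treatment group.
- **Unscheduled samples (8.8.12.4):** the investigator may repeat laboratory assessments at discretion. Nothing requires it.

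**The concern.** Safety and tolerability is the study's secondary objective, and an adverse event is the first withdrawal reason listed in 7.3. Subjects who leave during dosing are among those whose exit chemistry is of most interest, yet the schedule samples subjects who reach Day 8 and not those who leave before it.

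Two outputs are affected. The change-from-baseline and potentially clinically significant (PCS) summaries both need a postbaseline value. In addition, Sections 12.1 and 17.1 turn clinically significant out-of-range values into adverse events, so an absent sample also closes one route by which an adverse event would be found. This is a matter of collection rather than analysis: no analysis plan can recover a sample that was never drawn, and Section 7.4 does not replace subjects who withdraw.

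**Working it through.** **1. Scheduled samples for a subject dosed on Day 1/1a who leaves on Days 1-7.** The protocol states no figure on this point to reproduce, so the check is a walk through the schedule.

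| Occasion | Laboratory sample in Table 4 | After first dose | Reached by this subject |
|---|---|---|---|
| Screening | Yes | No | Yes |
| Day 8 | Yes | Yes | No |
| 9/ET | No | Yes | Yes, if the subject attends |
| Day 36 | Yes | Yes | No (8.5) |

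No row is at once sampled, post-dose and reached, so the count of scheduled post-dose samples is 0.

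**2. Is the row read correctly?** In the text copy of Table 4 some rows look displaced; randomization, for example, falls under Days -1 and 1. The laboratory row does not show this problem. Its Day 8 mark sits in the same column as the Day 8 marks for physical examination, residential discharge, naloxone challenge and VIVITROL injection, and its last mark falls on Day 36. The 9/ET cell is empty on that alignment.

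**3. Is there another scheduled route?** Sections 8.3.3.1 and 8.3.3.2 set the discharge procedures for subjects who do not transition to VIVITROL or who discontinue in the residential period. They add no laboratory sample. The only other route is discretionary testing under 8.8.12.4.

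**4. Does the subject still count?** Yes. One dose places the subject in the safety population. Without a postbaseline value the subject contributes no change from baseline and cannot be identified as having a PCS laboratory value.

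**5. How many could be affected?** The protocol gives no discontinuation rate for Days 1-7, so only a ceiling is available, and it rests on an assumption. Section 13.1 plans on 90% and 60% of subjects receiving and tolerating VIVITROL, with 46 per group. Anyone who leaves on Days 1-7 cannot meet that endpoint, so the expected number of early leavers cannot exceed the expected number of failures:

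- naltrexone + BUP: 46 × (1 − 0.90) = 4.6
- placebo + BUP: 46 × (1 − 0.60) = 18.4
- total: 4.6 + 18.4 = 23 of 92

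The range is therefore 0 to 23. It is an upper bound, because subjects with a positive naloxone challenge, or who tolerate the injection poorly, fail on or after Day 8 and are due the Day 8 sample.

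**The case against.** Several stronger readings are tempting, and the documents do not support them.

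- **That early leavers can never have laboratory data.** A reader might infer this from the schedule, but 8.8.12.4 allows discretionary repeats, and 7.3 requires ongoing adverse events to be followed to resolution or stability, with extended follow-up if needed. A subject who stops for an adverse event is the one most likely to be tested. The accurate statement is that no sample is scheduled. Symptom-driven testing is still not systematic and does not give comparable data across arms.
- **That the summaries describe only subjects who tolerated treatment.** Under 8.2.3 a subject who tolerates a dose poorly and misses the second one carries on with the next day's dosing, and subjects with a positive Day 8 challenge have also reached Day 8. The selection is on reaching Day 8, which is weaker than selection on tolerance.
- **That reported PCS incidence is diluted by a calculable amount.** That holds only if untested subjects are counted as not abnormal. Section 13.5 does not state the denominator, which may properly be left to the analysis plan. With tested subjects as the denominator the arithmetic dilution disappears, although the results still describe only those who were tested.
- **That the gap flatters naltrexone.** The only arm-specific rates are the planning rates. If early stops followed them, the loss would fall mainly on placebo. No direction can be asserted.
- **That the missing pregnancy test is part of the same loss.** The "Pregnancy Test" row of Table 4 also has no 9/ET mark, and the timing note reads "Urine pregnancy tests to be performed prior to randomization on Day 1/1a and prior to naloxone challenge on Day 8/8a", so a woman who leaves on Days 1-7 has no scheduled post-dose test. But that test is not part of the laboratory analysis in 13.5, and 8.9.4 makes separate provision for pregnancy. It is a separate safety-monitoring matter.

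What stands is the scheduling gap itself, which none of these points removes.

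**Conclusion.** The point holds as a gap in scheduled safety data. A dosed subject who discontinues on Days 1-7 has no scheduled post-dose laboratory sample. Unless discretionary tests are ordered, that subject is in the safety population but absent from the postbaseline laboratory results, which then rest on subjects who reached Day 8.

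The protocol does not give the number affected. The ceiling of 23 of 92 depends on the planning success rates being right and on every failure being an early stop, so it is not an estimate. The conclusion also rests on the column alignment of the laboratory row in Table 4, which should be confirmed against the laid-out table. The primary endpoint is untouched. The weight is that of a worthwhile, inexpensive correction to safety data capture that has to be made before the data are collected.

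**What to change.** In Section 7.3 and in the 9/ET column of Table 4, add biochemistry, hematology and urinalysis with an ET-only footnote, at least for subjects who leave before the Day 8 sample. Table 4 already uses this device for the PGART (note p), so Day 9 stays unchanged for everyone else. Days 1-7 are residential, so the sample could often be drawn before the subject leaves the unit. Those who leave abruptly and do not return for the ET visit would still be missed.

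A urine pregnancy test at ET for women is an optional, separate addition on safety-monitoring grounds.

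The cost is one routine blood and urine set per early leaver, at a visit already planned, plus a footnote and a clause in 7.3.
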